10.1.2 Vital Signs and Oxygen Saturation

Vital signs (blood pressure, heart rate, respiratory rate, and body temperature) and oxygen saturation will be monitored before and after administration of IMP, according to the Study Schedule of Events, [Table 1](#). Before vital signs and oxygen saturation are measured, the subject should rest for at least 5 minutes (if possible). The same position will be used each time vital signs and oxygen saturation are measured for a given subject.

10.1.3 Electrocardiograms

A standard 12-lead ECG will be performed at the various pre- and post-injection time points described in [Table 1](#). All ECG recordings will be read at the investigational site.

Each 12-lead ECG examination will be evaluated by a licensed physician. A physician reading ECGs may make clinical management decisions as needed.

Reference range limits for 12-lead ECG intervals are provided in Section [15.3](#). Each 12-lead ECG tracing must be signed and dated.

Interpretation and follow-up of interval data outside of reference ranges and abnormal waveforms should be conducted in conjunction with the clinical situation of the subject.

Each 12-lead ECG examination result at each time point (all intervals, heart rate and interpretation, and identified with the subject's initials, subject's study number, and date and time of recording), will be retained in the investigator's study record for each subject. The investigator will not be expected to calculate QTc intervals.

10.1.4 Physical Examination

A qualified physician will conduct physical examinations at the time points indicated in [Table 1](#). Where possible the same individual should conduct the physical examination at all required time points. The physical examination will include recording an assessment for the presence of abnormalities of the following: general appearance, skin, lungs, cardiovascular system, back and spine, abdomen, extremities, lymph nodes, and neurological exam.

In the event that *new* abnormal physical findings and *worsening* abnormal physical findings are encountered during the study, these terms are defined as follows: a new abnormal physical finding is defined as one that occurs when a subject's normal baseline physical examination becomes abnormal post baseline. A worsening abnormal physical finding is defined as one that occurs when a subject's abnormal baseline physical examination becomes worse post baseline.

10.1.5 Injection Site Monitoring

The injection site will be monitored at the times indicated in the Study Schedule of Events ([Table 1](#)).

Abnormal injection-site findings include, but are not limited to, radiopharmaceutical extravasation, bleeding, haematoma, redness, and infection. Abnormal injection site findings will be recorded as AEs in the CRF.

10.1.6 Tolerability Questionnaire Interview

Each subject is required to complete a tolerability questionnaire (see Appendix 15.4) at approximately 1 hour before injection and at approximately 15 minutes and 1, 4, 24, 48 hours after injection. The questionnaire evaluates subject mood, pain at injection site, itchiness of injection site, loss of function at injection site and quality of sleep using 100 mm visual analogue scales (VAS)* anchored by the following descriptors:

| | | |
|------------------------------------|--------------|--------------------------|
| Mood | Bad – 0mm | Good – 100mm |
| Pain at Injection Site | Normal – 0mm | Painful – 100mm |
| Itchiness of Injection Site | Normal – 0mm | Itchy – 100mm |
| Loss of Function at Injection Site | Normal – 0mm | Loss of Function – 100mm |
| Quality of Sleep | Bad – 0mm | Good – 100mm |

*Visual Analog Scale (VAS) is a continuous scale comprised of a horizontal line, usually 10 centimetres (100 mm) in length, anchored by 2 verbal descriptors: “0” stands for normal, and 100 mm stands for each symptom extreme, or “0” stands for bad, and 100 mm stands for good.

10.1.7 Adverse Events

All AEs/SAEs that occur after informed consent shall be recorded in the AE/SAE report form (see the Study Schedule of Events, [Table 1](#)).

Study personnel must remain vigilant for the occurrence of AEs, particularly those that may be life threatening. Personnel who are trained in the acute management of anaphylaxis and other emergencies and who have access to appropriate clinical supplies must be immediately available for no less than 60 minutes to observe for possible anaphylactoid reactions after dosing. Treatment of SAEs should be primarily supportive of vital functions.

An AE is defined as any untoward medical occurrence in a patient or clinical investigation subject which does not necessarily have to have a causal relationship with the IMP. AEs will be asked for from time of informed consent through the follow up visit at 2 weeks (\pm 2 days) after IMP administration.

A treatment-emergent AE (TEAE) is any unfavourable and unintended sign, symptom, or disease temporally associated with the use of DaTSCAN™, whether or not considered related to that product. Only symptoms/signs that begin or worsen in severity and/or frequency after DaTSCAN™-administration/use will be recorded as TEAEs in the CRF.

The subjects will be closely observed and questioned for any kind of AE during the study procedures and at follow-up appointments throughout the study period with non-leading questioning (e.g., “How do you feel?”). The subjects will be instructed to immediately report any symptoms and signs to the study staff.

Both the investigator(s) and sponsor/CRO will perform a causality assessment on any AE, to assess whether or not there is a reasonable possibility (evidence to suggest) that the IMP caused the event.

Causal relationship

Both the investigator(s) and sponsor/CRO will perform a causality assessment on any AE, to assess whether or not there is a reasonable possibility (evidence to suggest) that the IMP caused the event.

The relationship of an AE with DaTSCAN™ will be assessed and reported by the investigator as:

- Reasonably related to study drug (“Reasonable cause”): - A causal relationship between DaTSCAN™ and an AE is at least a reasonable possibility, i.e., the relationship cannot be ruled out.
- Not reasonably related to study drug (“Not reasonable cause”): - A causal relationship between DaTSCAN™ and an AE is not a reasonable possibility.

Expectedness

All DaTSCAN™-emergent AEs will be assessed, by the sponsor (or CRO on behalf of the sponsor), as to whether they were expected to occur or unexpected, meaning not anticipated based on current knowledge found in the applicable safety information included in the reference safety information in the Investigator Brochure (IB) for DaTSCAN™.

Unexpected: An unexpected DaTSCAN™-emergent AE is a reaction, for which the nature, seriousness, severity or outcome is not consistent with the applicable safety information included in the IB.

Expected: An expected DaTSCAN™-emergent AE is a reaction which is consistent with the applicable safety information included in the IB.

Adverse Reaction: An AE that is caused by the IMP.

Suspected Adverse Reaction: A suspected adverse reaction is an AE where reasonable possibility exists for causality between DaTSCAN™ and the AE.

10.1.8 Serious Adverse Events

An SAE is defined as any AE that:

- Results in death.
- Is life threatening.
- Requires inpatient hospitalisation or prolongation of existing hospitalisation.
- Results in persistent or significant disability or incapacity.
- Is a congenital anomaly or birth defect.
- Is another important medical event.*

(*Other important medical events are those that may not result in death, be life threatening, or require hospitalisation, but may be considered an SAE when, based upon appropriate medical judgment, they may jeopardise the subject and may require medical intervention to prevent one of the outcomes listed above.)

10.1.9 Other Significant Adverse Events

Clinically notable results from vital signs, clinical laboratory, and injection site findings should be reported as AEs, where applicable.

10.1.10 Adverse Event and Serious Adverse Event Reporting

All AEs should be recorded by using acceptable diagnoses, if possible. If an AE has already been reported, it is not necessary to report each individual sign and symptom of that AE as a separate AE. For example, if myocardial infarction is reported as an AE, there is no need to report elevated creatine kinase and abnormal ECG or other related signs, symptoms, or laboratory values as separate AEs. However, if both occurred in isolation and myocardial infarction was not diagnosed, then each event would be reported as an AE.

The intensity of all AEs will be graded as mild, moderate, or severe by using the following definitions:

| | |
|-----------|--|
| Mild: | Tolerable. |
| Moderate: | Interferes with normal activity. |
| Severe: | Incapacitating (causes inability to perform usual activity or work). |

The investigator will be instructed to closely monitor each subject who experiences an AE (whether ascribed to the IMP or not) until the outcome of the AE has been determined.

In addition to the investigator's own description of the AEs, each AE will be encoded by the sponsor/CRO according to a well-recognised dictionary of medical codes.

SAEs will be recorded in the CRF if they occur as follows:

- After a subject first signed informed consent and throughout the subject's follow-up period*, whether or not considered related to the IMP, and
- After the subject's follow-up period, and for which a causal relationship to the IMP cannot be ruled out.

(*Follow-up period is defined as the protocol-stipulated period or, for subjects prematurely withdrawn from a study, the duration of a subject's participation.)

All serious and non-serious AEs must be followed for a final outcome until the end of the follow-up period. An outcome of "unknown" is not considered to be an acceptable final outcome. An outcome of "not yet resolved" is an acceptable final outcome for non-serious AEs at the end of a subject's participation in a study, and for SAEs at database lock.

The investigator will report all SAEs to local authorities, sponsor, and IECs/ Institutional/Independent Review Boards (IRBs) as required by local regulations, sponsor standard operating procedures (SOPs), and site-specific IECs/IRBs. The CRO (on behalf of the sponsor) will report all SAEs to local health authorities, IECs/IRBs and investigators as required by local regulations and sponsor/CRO SOPs.

Study centres are instructed to report all SAEs (including DaTSCAN™-emergent SAEs), together with a causality assessment, to the sponsor (or a service provider/CRO acting on behalf of the sponsor) within 24 hours.

All AEs and SAEs are reported in the AE form of the CRF. Detailed information about management of AE information will be provided, e.g., in a Safety Management Plan or equivalent document.

SAE information will be captured in electronic data capture (EDC). If the EDC system is unavailable, the Investigators must complete an SAE form in English and forward it by fax to PPD Pharmacovigilance via at SAE [contact], immediately (within 24 hours) of becoming aware of the event.

Refer to the current SAE Form and Guidelines for completing and submitting the SAE form.

Requests for additional information will be made via the CRO personnel at the site.

Suspected unexpected serious adverse (drug) reactions will be reported to regulatory authorities, investigators, and IECs/IRBs in accordance with applicable legal requirements and applicable sponsor SOPs.

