6.2.2 Rationale for Safety Monitoring Plan

Safety assessments will be performed at screening, before and after administration of IMP, and approximately 2 weeks after administration of IMP. The planned safety assessments are designed to ensure subject safety and to identify and minimise unnecessary risks.

This study's safety monitoring plan is justifiable and adequate from a safety standpoint in view of the following:

- The design of the safety plan permits a comparison of the safety variables at baseline (in this study baseline period is defined as “after the screening visit up to 1 hour prior to administration” except clinical laboratory tests, of which baseline value is that taken during

screening visit) and after IV injection of DaTSCAN™ ioflupane (¹²³I) injection in the same subject.

- Safety variables collected in the present study can be compared with safety variables from other related studies.
- The 2-week safety monitoring permits the evaluation of late-appearing adverse events (AEs) that may emerge or progress after the administration of DaTSCAN™ ioflupane (¹²³I) injection.
- Evaluation of the safety database held by the sponsor (which includes clinical study data as well as post marketing data in the United States and Europe) does not show any new safety signals that would require a modification of the safety assessments as planned.
- The measures used to assess safety are well defined and reliable, and the proposed safety analyses are adequate to assess the effects of the administration of ioflupane (¹²³I) injection in HVs.

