7.4 Withdrawal and Termination Criteria

7.4.1 Subject Withdrawal

There are no formal withdrawal criteria for this study. During the conduct of the study, the sponsor or its designee will review the safety data for trends and signals that would indicate the need for withdrawal of a subject.

In accordance with the Declaration of Helsinki, each subject is free to withdraw from the study at any time. Investigator(s) also have the right to withdraw subjects from the study in the event of illness, AEs, or other reasons concerning the health or well-being of the subject, or in the case of lack of co-operation.

Should a subject decide to withdraw after administration of the IMP, or should the investigator(s) decide to withdraw the subject, all efforts will be made to complete and report the observations up to the time of withdrawal as thoroughly as possible. A complete final

evaluation at the time of the subject's withdrawal should be made and an explanation given of why the subject is withdrawing or being withdrawn from the study.

The reason for withdrawal must be noted in the Case Report Form (CRF). If the reason for withdrawal is an AE, the specific event or test result(s) must be recorded in the CRF. If the subject discontinues for a serious AE (SAE), such as hospitalization, the subject data will be collected and monitored until the outcome is evident. If the event has ended, the stop date of the event will be recorded in the CRF. If the event is still ongoing, the outcome of the event must be Ongoing or Not Yet Resolved. An outcome of Unknown is not acceptable, even if the event is ongoing on the date of study discontinuation.

Subjects who withdraw from the study before the study procedures are complete will be replaced.

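### For a dosed subject who withdraws early, 10.1.10 closes the follow-up period at withdrawal, in conflict with the 2-week adverse event questioning and safety assessment on which 6.1, 6.2.2 and 10.1.7 rely

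*Combined protocol and SAP*

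**What the plan says.** Section 10.1.10, in the footnote to its rule on recording serious adverse events (SAEs), reads: "Follow-up period is defined as the protocol-stipulated period or, for subjects prematurely withdrawn from a study, the duration of a subject's participation". The same section uses that period to limit outcome follow-up: "All serious and non-serious AEs must be followed for a final outcome until the end of the follow-up period". It also tells the investigator to "closely monitor each subject who experiences an AE (whether ascribed to the IMP or not) until the outcome of the AE has been determined", and it keeps SAEs arising "After the subject's follow-up period, and for which a causal relationship to the IMP cannot be ruled out".

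Section 7.4.1 says of a subject who leaves after dosing that "all efforts will be made to complete and report the observations up to the time of withdrawal", with a complete final evaluation at that time. For a subject who discontinues because of an SAE, "the subject data will be collected and monitored until the outcome is evident".

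Three other sections describe a 2-week window:
- 10.1.7: "AEs will be asked for from time of informed consent through the follow up visit at 2 weeks", give or take 2 days, with no exception for withdrawals.
- 6.2.2, as a reason why the safety plan is adequate: "The 2-week safety monitoring permits the evaluation of late-appearing adverse events (AEs) that may emerge or progress after the administration".
- 6.1: all subjects have safety assessments at the follow-up visit.

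On analysis, 12.2 puts every dosed subject in the safety set. Section 12.5.5 reports the number and percentage of subjects with at least one AE. Neither section mentions length of follow-up.

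**The concern.** Safety is the primary objective and the product is given once. Withdrawal after the injection therefore stops no further study drug; it only stops observation. If the 10.1.10 definition governs, a volunteer who leaves on day 1 or day 2 is never asked about the remaining days, yet counts in the AE table exactly like a volunteer seen for 2 weeks. With about 8 subjects, one unrecorded event is visible in the reported percentage. Site staff also have instructions that end at different times for the same subject.

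**Working it through.** The plan gives no dropout rate, event rate or sample size calculation bearing on this, so there is no figure of its own to reproduce. The check is a comparison of the text followed by conditional arithmetic.

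**1. What is captured after a dosed subject withdraws**

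| Event after withdrawal | Governing text | Captured? |
|---|---|---|
| New SAE, possibly related | 10.1.10, rule for SAEs after follow-up | Yes, no end date, but no contact is planned to find it |
| New SAE, judged unrelated | 10.1.10, follow-up period has ended | Not required |
| New non-serious AE | 10.1.7 says ask through 2 weeks; 7.4.1 and the 10.1.10 definition stop at withdrawal | Contradictory; no contact scheduled |
| Outcome of an AE already present | 10.1.10 (two wordings) and, for SAEs leading to discontinuation, 7.4.1 | Yes, although one wording in 10.1.10 stops at the end of follow-up |
| Pregnancy with conception within 30 days | 10.1.12, tied to exposure | Yes, if the subject reports it |
| 2-week laboratory tests and vital signs | 9.3 visit | No post-withdrawal visit is specified |

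**2. Share of the window observed**

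The withdrawal times are assumptions; the window is 14 days × 24 h = 336 h (9.3).
- Withdrawal at 6 h: 6/336 = 1.8%.
- Withdrawal at 24 h: 24/336 = 7.1%.
- Withdrawal at 48 h: 48/336 = 14.3%. With the visit at 12 days this is 48/288 = 16.7%; at 16 days it is 48/384 = 12.5%.

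**3. Effect on the AE percentage**

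The planned number is 8 (6.1). Section 7.4.1 replaces subjects who leave before procedures are complete, which makes 9 dosed if one is replaced. Suppose no other subject has an AE.
- No AE before leaving, one missed later: 1/8 = 12.5% becomes 0/8 = 0%. With a replacement, 1/9 = 11.1% becomes 0/9 = 0%.
- Withdrawn because of an AE: the subject is already counted, so the figure stays at 1/8 or 1/9. Only preferred-term and intensity counts could change.

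**4. Effect on what an absence of late events shows**

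With n subjects followed to 2 weeks and no late event, the one-sided 95% upper bound on the late-event rate is 1 − 0.05^(1/n).
- n = 8: 31.2%.
- n = 7: 34.8%.

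The chance of seeing at least one late event is 1 − (1 − p)^n, with p assumed:

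| p | n = 8 | n = 7 |
|---|---|---|
| 0.05 | 34% | 30% |
| 0.10 | 57% | 52% |
| 0.20 | 83% | 79% |

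If the withdrawn subject is replaced and the replacement completes, 8 are fully followed and the bound returns to 31.2%. The withdrawn subject nevertheless remains in the safety set with a shortened window.

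**The case against.** The best defence is that this is a wording gap with safeguards around it. The footnote is attached to the SAE-recording rule, AE questioning is governed by 10.1.7, and nothing expressly cancels the 9.3 visit for a withdrawn subject. A full evaluation is due at withdrawal. Laboratory abnormalities that are AEs are followed until their outcome is known (10.1.1), and an SAE may stay unresolved until database lock (10.1.10). Most scheduled safety assessments fall within 48 h, so the shares of clock time above do not measure risk. A Safety Management Plan, which is not part of these documents, may add detail.

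Much of this stands, and it rules out several stronger readings that a reader might infer:
- **That all later events are lost.** The table shows which are kept.
- **That AE percentages are biased because subjects withdrawn for AEs are cut short.** Those subjects already count under 12.5.5.
- **That withdrawn subjects dilute the 2-week laboratory and vital-sign summaries.** Section 12.1 reports n, and 12.6.5 and 12.10 treat missing values as missing. The subject drops out of those summaries, which rest on a smaller n.
- **That the primary outcome is itself defined over 2 weeks.** Section 10.1 counts AEs to study exit; the 2-week basis comes from 6.1, 6.2.2 and 10.1.7.
- **That those who withdraw are the subjects most likely to have late events.** Section 7.4.1 allows withdrawal for illness or AEs, but also by free choice or for lack of co-operation.

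The safeguards do not close the gap. They deal with AEs already present, possibly related SAEs and pregnancy. None provides a contact at which a new event would be asked about. The term defined in the footnote is also reused in the sentence limiting follow-up of all AEs, so its reach is not confined to SAE recording.

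**Conclusion.** The point holds in a limited form. A stated rule, not merely a missing detail, ends the follow-up period at withdrawal and conflicts with 6.1, 6.2.2 and 10.1.7. The outcome rules in 7.4.1 and 10.1.10 also stop at different times. What can go unrecorded is new non-serious AEs and new SAEs judged unrelated that start after withdrawal.

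The effect is at most one subject's worth of AE percentage per withdrawal: 12.5 points with 8 dosed, 11.1 with 9. It arises only if that subject had no earlier AE. These sizes rest on two assumptions that the documents do not inform: that a dosed subject withdraws, and that an event follows. It should be corrected because safety is the primary objective and correction is cheap; it does not by itself undermine the study.

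**What to change.** 1. In 10.1.10, define the AE and SAE collection period for every dosed subject as running through the 2-week (± 2 days) contact, whether or not the subject stops imaging or sampling, unless consent to further contact is withdrawn.
2. In 7.4.1, separate stopping study procedures from withdrawing consent to safety follow-up. For the former, use the existing 9.3 visit, or at least a telephone contact on AEs and concomitant medication.
3. Reconcile the outcome follow-up wording in 7.4.1 and 10.1.10 so that it ends at one stated time for each class of event.
4. Beside the AE table in 12.5.5, give the length of follow-up for any dosed subject observed for less than 2 weeks.

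The cost is an amendment, consent wording, and one already planned visit or a call per withdrawn subject. Some withdrawn volunteers will decline; item 4 then makes the shortfall visible.

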10.1.11 Urgent Safety Measures

In accordance with the principles of Good Clinical Practice (GCP) as laid out in ICH E6, the investigator(s) has/have primary responsibility for assuring subject safety throughout the performance of study procedures. An urgent safety measure is defined as any measure which

an investigator may need to implement which is a deviation from, or a change in, the protocol to eliminate an immediate hazard(s) to trial subjects without prior IEC/IRB approval/favourable opinion.

The investigator may take appropriate urgent safety measures in order to protect the subjects of a clinical trial against any immediate hazards to their health or safety. However, the investigator must inform the sponsor/CRO within 24 hours of having taken such measures.

The sponsor in turn shall immediately, and in any event no later than 3 days from the date the measures are taken, give written notice to the licensing authority and the relevant IEC/IRB of the measures taken and the circumstances giving rise to those measures.

All urgent safety measures must be reported to the sponsor/CRO by using the SAE contact numbers listed in Section 10.1.1 within 24 hours of having to take such a measure(s). Such reports can be initiated by telephone but must be officially documented by the investigator (by email or fax) and must include details of what measures were taken and the circumstances giving rise to those measures.

